To assess changes in concomitant medications of interest (including antihypertensive, anti-hyperglycemic, and lipid lowering agents) when switching to D/C/F/TAF FDC (Immediate Switch Arm) compared to continuing the current INI + TAF/FTC ARV regimen (Delayed Switch Arm)	 Proportion of participants having a dose-reduction or complete withdrawal of anti-hypertensive, anti-hyperglycemic, or lipid lowering agents in the Immediate Switch Arm or Delayed Switch Arm from Baseline to Week 24 Proportion of participants initiating an anti-hypertensive, anti-hyperglycemic, or lipid lowering agent in the Immediate Switch Arm or Delayed Switch Arm from Baseline to Week 24 					

Objectives	Endpoints
Safety	
To evaluate the safety of switching to D/C/F/TAF FDC (Immediate Switch Arm) compared to continuing the current INI + TAF/FTC ARV regimen (Delayed Switch Arm)	 Incidence of any Grade AEs (related and not related) through Week 24 Incidence of Grade 3 and 4 AEs (related and not related) through Week 24 Incidence of discontinuations due to AEs through Week 24 Incidence of SAEs (related and not related) through Week 24 Change from Baseline in clinical laboratory tests through Week 24 Incidence of Grade 3 and 4 laboratory abnormalities through Week 24
Efficacy	
To evaluate the virologic outcomes when switching to D/C/F/TAF FDC (Immediate Switch Arm) compared to continuing the current INI + TAF/FTC ARV regimen (Delayed Switch Arm)	 Proportion of participants with confirmed virologic rebound through Week 24 Proportion of participants with virologic response (HIV-1 RNA<50 copies/mL) at Week 24 according to the FDA snapshot algorithm Proportion of participants with virologic failure (HIV-1 RNA ≥50 copies/mL) at Week 24 according to the FDA snapshot algorithm Proportion of participants having virologic response (HIV-1 RNA<200 copies/mL) at Week 24 according to the FDA snapshot algorithm Proportion of participants having virologic failure (HIV-1 RNA ≥200 copies/mL) at Week 24 according to the FDA snapshot algorithm
To evaluate immunological changes when switching to D/C/F/TAF FDC (Immediate Switch Arm) compared to continuing the current INI + TAF/FTC ARV regimen (Delayed Switch Arm) Resistance	Change from Baseline in CD4+ cell count at Week 24
	Donation of auticipants with any baseline DD DT and DH

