 - o Tricyclic antidepressants; eg: amitriptyline, doxepin, imipramine, nortriptyline, trimipramine.
 - o Selective Serotonin Reuptake Inhibitors; eg: sertraline, paroxetine, fluvoxamine.
 - o Antipsychotics; eg: haloperidol, loxapine, clozapine, chlorpromazine, fluphenazine, risperidone, olanzapine, quetiapine.
 - o Antiseizure/Anticonvulsants; ie, Valproic acid, carbamazepine, gabapentin, topiramate, zonisamide, lamotrigine.
 - Others: bupropion, nefazodone, lithium, mirtazapine.
- Steroid Hormones: chronic oral corticosteroids at an equivalent ≥5 mg of prednisone orally a day
 - o Use of a methylprednisolone dose pack or use of acute steroids for treatment of allergic reactions for ≤7 days are not exclusionary.
- Hormone therapy/contraception; eg: estrogen, testosterone, progestogens, tesamorelin.
- Appetite Stimulants/Suppressants; eg: phentermine, topiramate, methylphenidate, amphetamine/dextroamphetamine, megestrol, oxandrolone, dronabinol.
- 12. receiving ongoing therapy with contraindicated drugs within 30 days of screening, not recommended drugs that cannot be adequately dose-adjusted, or participants with any known allergies to the excipients of the D/C/F/TAF FDC tablet.
- 13. current alcohol or substance use judged by the investigator to potentially interfere with participant study adherence or changes in body weight.
- 14. known, active, severe infections (other than HIV-1 infection) requiring parenteral antibiotic or antifungal therapy within 30 days prior to baseline.

- 15. received an investigational intervention (including investigational vaccines) or used an invasive investigational medical device within 90 days of baseline or is currently enrolled in an investigational study without prior approval from the sponsor.
- 16. pregnant, or breast-feeding, or planning to become pregnant while enrolled in this study or within 90 days after the last dose of study intervention.
- 17. plans to father a child while enrolled in this study or within 90 days after the last dose of study intervention.
- 18. any other condition or prior therapy for which, in the opinion of the investigator, participation would not be in the best interest of the participant (eg, compromise the well-being) or that could prevent, limit, or confound the protocol-specified assessments.

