6.8. Concomitant Therapy

Prestudy therapies including all previous ARV treatments and non-ARV treatments received up to twelve months before Screening must be recorded.

Concomitant therapies must be recorded throughout the study beginning with Screening up to the last dose of study intervention. Concomitant therapies should also be recorded beyond the last study visit only in conjunction with new or worsening AEs, SAEs that meet the criteria outlined in Serious Adverse Events in Section 8.3.1, Time Period and Frequency for Collecting AEs and SAE Information.

All therapies (prescription or over-the-counter medications, including vaccines, vitamins, herbal supplements; non-pharmacologic therapies such as electrical stimulation, acupuncture, special diets, exercise regimens) different from the study intervention must be recorded in the case report form (CRF). Recorded information will include a description of the type of therapy, duration of use, dosing regimen, route of administration, and its indication. Modification of an effective preexisting therapy should not be made for the explicit purpose of entering a participant into the study if such modification of treatment is not clinically acceptable. Any change in dosage of the medication must be reported in the electronic CRF (eCRF).

For those participants with treatment emergent hyperglycemia, hypertension or dyslipidemia, initiation of medications to address these AEs should be prescribed in accordance to national treatment guidelines (See Figure 4 in Appendix 9: Characteristics, Prevention, and Management of Cardiovascular Diseases in People Living with HIV by American Heart Association; page 14: Figure 4 in Appendix 10: 2017 American College of Cardiology (ACC) Guideline for the Prevention, Detection, Evaluation, and Management of High Blood Pressure in Adults; and page 6: Figure 2 in

Appendix 11: Management of Hyperglycemia in Type 2 Diabetes, 2018. A Consensus Report by the American Diabetes Association (ADA) and the European Association for the Study of Diabetes (EASD)]).

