Investigators are reminded that certain medications may influence body weight changes or may be contraindicated and should be avoided (see disallowed concomitant therapy below and Exclusion Criteria No. 11). Should a participant have a need to initiate treatment with any excluded concomitant medication, it is recommended that investigators consult with the sponsor medical monitor beforehand to determine if an alternative therapy could be utilized that has no known impact on weight or if the participant should be discontinued from the study. If an excluded medication is initiated before discussion with the medical monitor, the investigator must notify the sponsor as soon as becoming aware.

Participants who experience clinically significant changes in body weight during the course of the study may require dose reductions or withdrawal of medications to treat hypertension, type II diabetes, or hyperlipidemia in order to avoid events such as hypoglycemia, hypotension, etc. As part of routine care at scheduled follow-up visits, participants should be assessed to determine if a dose reduction or withdrawal of medications for the treatment of such conditions is warranted. These changes will be recorded in the CRF.

Contraindicated and Disallowed Concomitant Agents

DRV co-administered with COBI is an inhibitor of CYP3A, CYP2D6, and P-glycoprotein (P-gp). Cobicistat also inhibits the transporters breast cancer resistance protein (BCRP), multi-antimicrobial extrusion protein (MATE)-1, organic anion-transporting polypeptide (OATP)1B1 and OATP1B3. Cobicistat is not expected to inhibit CYP1A2, CYP2B6, CYP2C8, CYP2C9 or CYP2C19. Cobicistat is not expected to induce CYP1A2, CYP3A4, CYP2C9, CYP2C19, uridine diphosphate glucuronosyltransferase 1A1 (UGT1A1), or multidrug resistance protein 1 (MDR1).

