D/C/F/TAF FDC tablet should not be co-administered with medicinal products that are highly dependent on CYP3A for clearance and for which increased plasma concentrations are associated with serious and/or life-threatening events (narrow therapeutic index). These medicinal products include alfuzosin, astemizole, carbamazepine, cisapride, colchicine (in participants with renal and/or hepatic impairment), dronedarone, elbasvir/grazoprevir, ergot alkaloids (eg, dihydroergotamine, ergotamine, ergonovine and methylergonovine), lomitapide, lovastatin, lurasidone, oral midazolam, phenobarbital, phenytoin, pimozide, ranolazine, rifampin, sildenafil (when used for treatment of pulmonary arterial hypertension), simvastatin, St John's Wort, terfenadine, and triazolam.

Emtricitabine is not an inhibitor of human CYP450 enzymes. In vitro and clinical drug interaction studies have shown that the potential for CYP-mediated interactions involving FTC with other medicinal products is low. Emtricitabine is primarily excreted by the kidneys by a combination of glomerular filtration and active tubular secretion. No drug interactions due to competition for renal excretion have been observed; however, coadministration of FTC with drugs that are eliminated by active tubular secretion may increase concentrations of FTC and/or the co-administered drug. Drugs that decrease renal function may increase concentrations of FTC.

CONFIDENTIAL – FOIA Exemptions Apply in U.S.

Tenofovir alafenamide is a substrate of the efflux transporter P-gp. Drugs that induce P-gp activity are expected to decrease the absorption of TAF, resulting in decreased plasma concentrations of TAF, which may lead to loss of therapeutic effect of D/C/F/TAF FDC tablet and development of resistance. These medicinal products include antimycobacterials (rifabutin, rifampin, rifapentine) and anticonvulsants (carbamazepine, oxcarbazepine, phenobarbital, phenytoin). Coadministration of D/C/F/TAF FDC tablet with drugs that inhibit P-gp may increase the absorption and plasma concentration of TAF.

Given the possibility for PK interactions, investigators should refer to the IB for the D/C/F/TAF FDC tablet and individual Prescribing Information for the components of the D/C/F/TAF FDC tablet for potential contraindications and management of drug interactions to preserve participant safety during the study.

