Refer to the current individual agents' PI of the continued INI + TAF/FTC ARV regimen for guidance with regard to dose adjustments for concomitant use with other medications, and for contraindicated medications or medications that are not recommended for concomitant use.

All contraindicated or disallowed medications must be discontinued at least 30 days before the Screening Visit (Day 1) and for the duration of the study. If such discontinuation of treatment is not clinically acceptable, the participant should not be allowed to participate in the study.

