6.2. Secondary Endpoints and Analysis Methods

6.2.1. Weeks 24 and 48 Endpoints

In the following, the secondary endpoints at Week 24 are defined for D/C/F/TAF FDC regimen (Immediate Switch Arm) versus INI + TAF/FTC ARV regimen (Delayed Switch Arm), while the secondary endpoints at Week 48 are related to D/C/F/TAF FDC (Immediate Switch Arm) only.

Metabolic:

- Change from Baseline in absolute body weight over time
- Proportion of participants with % change from baseline in body weight >5% over time.
- Proportion of participants with % change from baseline in body weight >3% over time.
- Change from Baseline in BMI over time.
- Change from Baseline in body composition as measured by DEXA scan at Week 24 and Week 48, respectively.
- Change from Baseline in waist circumference over time.
- Change in SBP and DBP from Baseline over time.
- Change from Baseline in fasting lipids over time.
- Change from Baseline in fasting glucose over time.
- Change from Baseline in HOMA-IR at Week 24 and Week 48, respectively.
- Change from Baseline in HbA1c at Week 24 and Week 48, respectively.
- Change from Baseline in leptin and adiponectin at Week 24 and Week 48, respectively.
- Change from Baseline in the proportion of participants with advanced fibrosis according to the NAFLD fibrosis score at Week 24 and Week 48, respectively.
- Change from Baseline in the proportion of participants at high risk of NASH according to the HAIR score at Week 24 and Week 48, respectively.
- Proportion of participants having a dose-reduction or complete withdrawal of anti-hypertensive, anti- hyperglycemic, or lipid lowering agents in the Immediate Switch Arm from Baseline to Week 24 and Week 48, respectively or Delayed Switch Arm from Baseline to Week 24.
- Proportion of participants initiating an anti-hypertensive, anti-hyperglycemic, or lipid lowering agent in the Immediate Switch Arm from Baseline to Week 24 and Week 48, respectively or Delayed Switch Arm from Baseline to Week 24.

Safety:

- Incidence of any Grade AEs (related and not related) through Week 24 and Week 48, respectively.
- Incidence of Grade 3 and 4 AEs (related and not related) through Week 24 and Week 48,

- respectively.
- Incidence of discontinuations due to AEs through Week 24 and Week 48, respectively.
- Incidence of SAEs (related and not related) through Week 24 and Week 48, respectively.
- Change from Baseline in clinical laboratory tests over time.
- Incidence of Grade 3 and 4 laboratory abnormalities over time.

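### The medication-reduction endpoint counts changes whatever their cause, so adjustments for darunavir/cobicistat interactions can appear as a metabolic difference in the Immediate Switch Arm

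*Protocol*

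**What the plan says.** Protocol 3.1 lists, under the metabolic objectives at Week 24, the "Proportion of participants having a dose-reduction or complete withdrawal of anti-hypertensive, anti-hyperglycemic, or lipid lowering agents" in either arm. A companion endpoint counts participants who start such an agent. Protocol 3.2 repeats both at Week 48 for the Immediate Switch Arm. SAP 6.2.1 carries the definition over ("Proportion of participants having a dose-reduction or complete withdrawal of anti-hypertensive" and so on). SAP 6.2.1.1 reuses it to compare the Immediate Switch Arm up to Week 24 with the Delayed Switch Arm from Week 24 to Week 48. None of these places conditions the count on a reason.

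On interactions, Protocol 6.8 describes darunavir with cobicistat as an inhibitor of CYP3A, CYP2D6 and P-gp, and adds several transporters for cobicistat. Its list of drugs not to be co-administered includes three lipid-lowering agents: lomitapide and lovastatin ("lomitapide, lovastatin, lurasidone, oral midazolam") and, later in the same list, simvastatin. It then requires: "All contraindicated or disallowed medications must be discontinued at least 30 days before the Screening Visit (Day 1". For other interactions it sends investigators to the Investigator's Brochure and the Prescribing Information "for potential contraindications and management of drug interactions to preserve participant safety during the study".

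Exclusion criterion 12 (Protocol 5.2) has two relevant parts. It bars ongoing therapy with contraindicated drugs within 30 days of screening, and it bars "not recommended drugs that cannot be adequately dose-adjusted".

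**The concern.** The endpoint sits with the metabolic outcomes, and Protocol 6.8 explains why such reductions are expected: a participant whose weight changes materially may need less treatment for hypertension, diabetes or hyperlipidemia. A reader of the Week 24 table will therefore tend to take a higher proportion in the Immediate Switch Arm as a sign of metabolic improvement.

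Starting darunavir/cobicistat is a second possible cause of the same recorded event. Inhibiting a drug's clearance raises its concentration, so adjustments made for that reason would tend to be downward or to be replacements. Up to Week 24 that trigger is new in one arm only. If such changes occur, part of the difference between arms would reflect pharmacology, and the definition gives no way to tell how much.

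**Working it through.** The documents give no planned rate, power or sample size for this endpoint. The only design figure used below is 55 per arm, which follows from the plan's own formula for the primary endpoint: 16/ES² = 16/0.54² = 54.9, so 55.

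**Which changes can fall in the counting window**

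1. *Contraindicated agents.* Exclusion 12 and the washout in Protocol 6.8 apply before randomization and so to both arms. Withdrawals of lovastatin, simvastatin and lomitapide fall before Baseline and are not counted. The washout sentence labels the Screening Visit as Day 1, whereas the Schedule of Activities uses Day 1 for Baseline. The two should be reconciled, but either reading puts the stop before Baseline.
2. *Interacting agents that can be dose-adjusted.* Exclusion 12 leaves these in. Allocation becomes known on Day 1 and the Immediate Switch Arm starts within 24 hours of the Baseline visit (Protocol 4.1). SAP 2.7 takes baseline as the last observation before first intake or randomization. An adjustment made once treatment starts is therefore a post-baseline change and is counted.
3. *The comparator.* The Delayed Switch Arm continues a regimen already taken for at least 6 months (inclusion criterion 4.1) and has no new trigger of this kind until it starts D/C/F/TAF after Week 24.
4. *The consistency comparison.* Both windows compared in SAP 6.2.1.1 open with the start of D/C/F/TAF. The same adjustments can occur in each, so agreement between them does not separate the two causes.
5. *Data to separate the causes.* Protocol 6.8 requires dose changes to be reported. The items it lists are type of therapy, duration, dosing regimen, route and indication; a reason for change is not among them.
6. *Substitution.* Neither document says whether the unit is the agent or the drug class. Counted by agent, replacing one antihypertensive with another is both a withdrawal and an initiation. Counted by class, it is neither.

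**How the artefact would scale**

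Let p0 be the proportion in each arm with a reduction or withdrawal for other reasons, and q the proportion of the Immediate Switch Arm with an interaction-driven one. Assume the two are independent and that the switch has no metabolic effect. Then:

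- Immediate Switch Arm proportion = 1 − (1 − p0)(1 − q)
- Spurious difference = q(1 − p0)

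Both inputs are assumptions:

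| p0 | q | Immediate vs Delayed | Difference (points) | Extra participants of 55 |
|---|---|---|---|---|
| 5% | 5% | 9.75% vs 5% | 4.75 | 2.6 |
| 5% | 10% | 14.5% vs 5% | 9.5 | 5.2 |
| 5% | 20% | 24.0% vs 5% | 19.0 | 10.45 |
| 10% | 5% | 14.5% vs 10% | 4.5 | 2.5 |
| 10% | 20% | 28.0% vs 10% | 18.0 | 9.9 |

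The table shows only that the spurious difference is close to q itself. It does not estimate q, which could be near zero.

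**The case against.** The strongest counter-argument is that the clearest interactions named in the documents are already handled. The washout removes the contraindicated lipid-lowering drugs before Baseline. What remains depends on permitted agents whose dose must fall with darunavir/cobicistat, and the documents name none; they refer to labels that are not part of them. This stands, and it limits how much can be claimed.

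Several further points also carry weight:

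- The stated objective is neutral: it is to assess changes in these medications. Calling a reduction a benefit is the reader's inference, though one that the placement under metabolic outcomes and the explanation in Protocol 6.8 encourage.
- If a swap counts as a withdrawal, it also appears in the initiation endpoint, so the two read together would hint at substitution. Simple dose reductions have no such counterpart, so this offset is partial.
- For diabetes drugs, most classes are on the exclusion 11 list, and Protocol 6.8 and 8.2.6.6 discourage starting them on study. That limits swaps in this class.
- The endpoint is descriptive (SAP 6.2.2.1), as is the consistency comparison (Protocol 3.3). No test is planned, so a false-positive rate for it would describe nothing in the plan.
- Recording a reason brings in judgement by investigators who know the treatment. This is a fair argument against replacing the all-cause count, but not against adding a separate row beside it.

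**Conclusion.** The concern holds in a limited form. The definition is blind to cause in both documents, a cause unrelated to metabolism is introduced in one arm only up to Week 24, and the planned consistency comparison would repeat the artefact. The direction, toward more reductions in the Immediate Switch Arm, follows from the inhibition described in Protocol 6.8. It rests on the inference that at least some participants take permitted agents that are adjusted when D/C/F/TAF starts.

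The size cannot be estimated. A reader might multiply a guessed share of users by a guessed share needing adjustment and quote the product as the bias; the documents support neither factor. Nor do they support reading exclusion 12 as barring only drugs that cannot be adjusted, since it separately bars contraindicated ones. They do not state that counting is by agent. Any effect should be smaller in participants entering on EVG/C/FTC/TAF, a regimen listed in SAP 2.5, because they already take cobicistat. The primary weight analysis does not use this endpoint and is unaffected. This is a matter of interpreting one secondary metabolic endpoint, and worth correcting because the correction is small.

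**What to change.** - Keep the all-cause tabulation as planned.
- Add a reason-for-change item to the concomitant-medication eCRF page.
- In SAP 6.2.1 and 6.2.1.1, add a row that separates changes made because of an interaction with study treatment. An alternative that needs no new data field is a sensitivity tabulation excluding agents with a labelled darunavir/cobicistat interaction.
- State the counting unit, and define same-class substitution as neither a withdrawal nor an initiation.

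The cost is one extra eCRF item (or a check of recorded agents against the labels), some open-label judgement in the recorded reason, and a lower event count once interaction-driven changes are separated out. No treatment rule changes.

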3.2. Week 48 Objectives and Endpoints

Objectives	Endpoints
Secondary Metabolic	
To assess the percent change in body weight when switching to D/C/F/TAF FDC (Immediate Switch Arm)	Percent change from Baseline in body weight at Week 48
• To assess change in body weight when switching to D/C/F/TAF FDC (Immediate Switch Arm)	 Change from Baseline in absolute body weight at Week 48 Proportion of participants with % change in body weight >3% at Week 48 Proportion of participants with % change in body weight >5% at Week 48 Change from Baseline in BMI at Week 48
• To assess changes in body composition when switching to D/C/F/TAF FDC (Immediate Switch Arm)	 Change from Baseline in body composition as measured by DEXA scan at Week 48 Change from Baseline in waist circumference at Week 48
To assess change in blood pressure when switching to D/C/F/TAF FDC (Immediate Switch Arm)	Change in SBP and DBP from Baseline at Week 48
• To assess changes in clinical laboratory tests when switching to D/C/F/TAF FDC (Immediate Switch Arm)	 Change from Baseline in fasting lipids at Week 48 Change from Baseline in fasting glucose at Week 48 Change from Baseline in HOMA-IR at Week 48 Change from Baseline in HbA1c at Week 48 Change from Baseline in leptin and adiponectin at Week 48
 To assess changes in liver biomarkers when switching to D/C/F/TAF FDC (Immediate Switch Arm) 	 Change from Baseline in the proportion of participants with advanced fibrosis according to the NAFLD fibrosis score at Week 48 Change from Baseline in the proportion of participants at high risk of NASH according to the HAIR score at Week 48
• To assess changes in concomitant medications of interest (including antihypertensive, anti-hyperglycemic, and lipid lowering agents) when switching to D/C/F/TAF FDC (Immediate Switch Arm)	 Proportion of participants having a dose-reduction or complete withdrawal of anti-hypertensive, anti-hyperglycemic, or lipid lowering agents in the Immediate Switch Arm from Baseline to Week 48 Proportion of participants starting an anti-hypertensive, anti-hyperglycemic, or lipid lowering agent in the Immediate Switch Arm from Baseline to Week 48
Safety	
To evaluate the safety of switching to D/C/F/TAF FDC (Immediate Switch Arm)	 Incidence of any Grade AEs (related and not related) through Week 48 Incidence of Grade 3 and 4 AEs (related and not related) through Week 48 Incidence of discontinuations due to AEs through Week 48 Incidence of SAEs (related and not related) through Week 48 Change from Baseline in clinical laboratory tests through Week 48 Incidence of Grade 3 and 4 laboratory abnormalities through Week 48
Efficacy	
To evaluate the virologic outcomes when switching to D/C/F/TAF FDC (Immediate Switch Arm)	Proportion of participants with confirmed virologic rebound through Week 48

Objectives	Endpoints
	 Proportion of participants with virologic response (HIV-1 RNA<50 copies/mL) at Week 48 according to the FDA snapshot algorithm
	 Proportion of participants with virologic failure (HIV-1 RNA ≥50 copies/mL) at Week 48 according to the FDA snapshot algorithm
	 Proportion of participants having virologic response (HIV-1 RNA<200 copies/mL) at Week 48 according to the FDA snapshot algorithm
	 Proportion of participants having virologic failure (HIV-1 RNA ≥200 copies/mL) at Week 48 according to the FDA snapshot algorithm
To evaluate immunological changes when switching to D/C/F/TAF FDC (Immediate Switch Arm)	Change from Baseline in CD4+ cell count at Week 48
Resistance To assess viral resistance in participants with confirmed HIV-1 RNA rebound when switching to D/C/F/TAF FDC	Incidence of observed genotypic and phenotypic ARV resistance for participants meeting HIV-1 RNA rebound criteria through Week 48
	Proportion of participant with newly identified post-baseline RAMs and phenotypic resistance compared to pre-baseline resistance tests when available, upon meeting confirmed virologic rebound through Week 48
PROs	T
To assess changes in the burden of common symptoms associated with HIV treatment or disease for participants	• Change from Baseline in the proportion of participants who have bothersome symptoms (scores of 2, 3 or 4) across all items of the HIV-SI at Week 48
switching to D/C/F/TAF FDC (Immediate Switch Arm)	• Change from Baseline in the proportion of participants who have any symptoms (scores of 1, 2, 3 or 4) across all items of the HIV-SI at Week 48
To describe responses on the PGIC in participants switching to D/C/F/TAF FDC (Immediate Switch Arm)	PGIC at Week 48
Adherence	1
To evaluate adherence in participants switching to D/C/F/TAF FDC (Immediate Switch Arm)	 Adherence rates by participant self-report using 4-day recall at Weeks 36 and 48
Exploratory	
Exploratory clinical biomarker	
To assess changes in alpha melanocyte-stimulating hormone when switching to D/C/F/TAF FDC (Immediate Switch Arm)	Change from Baseline in alpha melanocyte-stimulating hormone at Week 48
Exploratory PROs	
To assess changes in eating-related concepts (hunger, appetite, cravings, and satiety) for participants switching to D/C/F/TAF FDC (Immediate Switch Arm)	Change from Baseline in the scores on the DAILY EATS at Week 48
To assess changes in concerns about body shape for participants switching to	• Change from Baseline in the scores on the BSQ-8D at Week 48

CONFIDENTIAL – FOIA Exemptions Apply in U.S.

Objectives	Endpoints
D/C/F/TAF FDC (Immediate Switch Arm)	• Change from Baseline in the proportion of participants who have no concern (<19), mild concern (19-25), moderate concern (26-33) or marked concern (>33) with their body shape on the BSQ-8D at Week 48

Abbreviations: AE: adverse event, ARV: antiretroviral, BMI: body mass index, BSQ 8D: body shape questionnaire, D/C/F/TAF FDC: Darunavir/Cobicistat/Emtricitabine/Tenofovir Alafenamide Fixed dose Combination, DBP: diastolic blood pressure, DEXA: dual energy X ray absorptiometry, FDA: Food Drug Administration, FTC: emtricitabine, HAIR: hypertension, age, insulin, resistance, HIV 1 RNA: human immunodeficiency virus type 1 ribonucleic acid, HIV SI: HIV Symptom Index, HOMA IR: homeostatic model assessment of insulin resistance, INI: integrase, NAFLD: non alcoholic fatty liver disease, NASH: Nonalcoholic fatty liver disease, PGIC: patient global impression of change, PR: protease, PROs: patient reported outcomes, RT: reverse transcriptase, SAE: serious adverse event, SBP: systolic blood pressure.

3.3. Consistency of Effect of Baseline to Week 24 (Immediate Switch) versus Week 24 to Week 48 (Delayed Switch)

Additional secondary objectives/endpoints will evaluate the consistency of effect on outcomes from Baseline to Week 24 in the Immediate Switch Arm versus the Week 24 to Week 48 in the Delayed Switch Arm. The endpoints for the Delayed Switch Arm from Week 24 to Week 48 are the same as for the Immediate Switch to Week 24. Comparison will be made descriptively to evaluate the consistence of outcomes between these two arms for each endpoint.

Refer to Section 8, Study Assessments and Procedures for evaluations related to endpoints.

HYPOTHESIS

Based on the primary endpoint, the percent change in body weight at Week 24 from baseline in the Immediate Switch Arm is less than that of the Delayed Switch Arm (INI + TAF/FTC ARV).

